#### 8.9. Limitations of the Research Methods

The main strength of this study is the nation- and patient-wide coverage of the cohort. The study is expected to include all 21 health care districts in Finland. The data is also versatile as it is derived from the patient information systems in the hospital districts.

The main limitation of the study are its' retrospective nature and the expected number of observations (approximately 100-150 patients). Therefore, some sub-group or stratified analyses are not necessarily possible. It is also likely that the data is partially incomplete because of the variation between hospitals. All variables or sum variable components are not necessarily available from different electronical health records. To a citinib has been used in Finland for a rather short time so data for all endpoints at all timepoints may not be calculated/available. As in the registry studies in general the primary data source (hospital electronic health record [EHR]) in this study may be prone to potential human errors. Data is subject to gaps and human errors made by physicians entering data into the system.

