Fecal calprotectin	Primary objective 7.2.1.d, Secondary objectives 7.3.1.g and 7.3.1.h.	mg/kg
Plasma CRP	Primary objective 7.2.1.d Secondary objective 7.3.1.t	mg/L
Blood hemoglobin	Primary objective 7.2.1.d, Secondary objective 7.3.1.u	g/L
Blood leukocytes	Primary objective 7.2.1.d Secondary objective 7.3.1.v	cells/L
Blood thrombocytes	Primary objective 7.2.1.d Secondary objective 7.3.1.w	cells/L
Blood lymphocytes	Primary objective 7.2.1.d Secondary objective 7.3.1.x	cells/L
Blood neutrophiles	Primary objective 7.2.1.d Secondary objective 7.3.1.y	cells/L
Plasma albumin	Primary objective 7.2.1.d Secondary objective 7.3.1.z	g/L
Tofacitinib dose	Secondary objectives 7.3.1.a, 7.3.1.aa and 7.3.1.bb	mg*times/per day or "not on treatment"
Colectomies	Secondary objective 7.3.1.cc	Date
Type of healthcare contact	Secondary objective 7.3.1.cc	outpatient visit, remote contact, emergency visit or hospitalization

Variable	Role	Operational definition
Prior IBD treatments	Secondary objective 7.3.2	Yes/no (For each treatment)
 corticosteroids 5-aminosalicylic acid (5-ASA) azathioprine 6-mercaptopurine methotrexate cyclosporine ustekinumab vedolizumab adalimumab infliximab golimumab 		
Concomitant medications o corticosteroids o 5-ASA	Secondary objective 7.3.1.q,	product & dose
Extraintestinal manifestations: arthralgia, arthritis, sacroiliitis, pyoderma gangrenosum, erythema nodosum, primary sclerosing cholangitis, uveitis, ankylosing spondylitis, aphthous stomatitis, psoriasis	CCI	Yes/no per pre-specified list
Prior diagnoses	CCI	Yes/no per pre-specified list
Death date or lost to follow up	Used to define end of follow up	Date

Further operational definitions from the collected data include:

Active disease:

• An endoscopic Mayo sub-score of ≥ 2 or fecal-calprotectin (f-calpro) > 250 mg/kg.

Clinical response:

• A full Mayo score decrease of ≥ 3 points and a decrease of $\geq 30\%$ from baseline, with a decrease of ≥ 1 point on the rectal bleeding subscore or an absolute rectal bleeding score of ≤ 1 .

• A partial Mayo score (ie, Mayo score without endoscopic assessment) decrease of ≥2 points and reduction of at least 25% in partial Mayo (pMayo) score from baseline with an accompanying decrease in rectal bleeding sub score of ≥1 point or absolute rectal bleeding sub score of ≤1.

Clinical remission:

- A full Mayo score of ≤ 2 points with no individual sub score exceeding 1 point, with rectal bleeding sub-score of 0.

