6 HANDLING OF MISSING VALUES

No imputation for missing values will be performed. Proportion of missing values will be reported where appropriate.

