7 STATISTICAL METHODOLOGY AND STATISTICAL ANALYSES

7.1 STATISTICAL METHODS

General:

Means, medians, and standard deviations, and 25% and 75% quartiles will be provided for continuous variables when performing descriptive analysis of continuous data. Numbers and percentages will be provided for dichotomous and polychotomous variables when performing descriptive analysis of categorical data.

Serial measures collected will be handled by "carry forward imputation", i.e. the latest value will be assumed unchanged until otherwise proven. Thus for each timepoint, the latest available measure will be used. Patients will be censored from the study post the last available contact/data entry. Missing values will not be imputed.

An unadjusted Kaplan Meier curve will be drawn to illustrate time-to-event and to estimate medians for time-to-event outcomes.

All data analysis will be executed using R, a language and environment for statistical computing and graphics, version 4.0.3 or later in Rstudio environment.

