7.2 STATISTICAL ANALYSES

Primary objectives a-e:

Describe the patient population at the baseline (initiation of tofacitinib), using the data collected. For each continuous variables (age, BMI, age at diagnosis, duration of disease, laboratory measures), provide the mean, median, sd, 25%Q and 75%Q values. For categorical variables (sex, smoking status, extent of colonic involvement, disease severity, endoscopic findings), report the number of patients, and proportion. Report proportion of missing values if present.

Secondary objective - Assess the Real-world Effectiveness of Tofacitinib

Secondary objective a:

For each patient, define the "on treatment" as Yes/No based on the latest available dose (at each timepoint 8, 16, 24 and 52 weeks). Patients marked with "not on treatment" prior to timepoint will be regarded as discontinued.

Report the proportion of patients on treatment, not censored at each timepoint.

Secondary objectives b, c, d, e, g, n:

For each patient, define the fulfilment of the remission/response criteria as Yes/No based on the latest available data (at each timepoint 8, 16, 24 and 52 weeks).

Report the proportion of patients on fulfilling the response/remission criteria, not censored at each timepoint.

Secondary objective f:

Define the time of response for each patient as first ever data-entry that fulfils response criteria. Fit competing-risk time-to-event model to the data, with time-to-event defined as time from index until response (event) or discontinuation (competing event), or end of data collection (censoring event).

Assess the cumulative incidence as function of time for both types of events. Illustrate the Aalen-Johansen state probabilities of multistate model.

Secondary objective h:

Select only patients with baseline f-calprotectin above 250 mg/kg at baseline. For each subsequent f-calprotectin measure, define below 250 mg/kg as Yes/No variable. Additionally, estimate the absolute delta change per baseline value.

For each timepoint (week 8, 16, 24 and 52), report the proportion of patients on fulfilling the <250mg/kg criteria, and summary statistics (mean, median, sd, 25%Q and 75%Q) of delta change, among patients not censored at each timepoint.

Secondary objectives i, j, k, m, o:

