8 TABLE SHELLS

Table 2: Table shell for patient characteristics for primary objective

				n	missing
Variable	categories	mean (sd)	Median (25Q-75Q)	(%)	%
age				-	
sex	male	-	-		
	female	-	-		
weight				-	
height				-	
(BMI)				-	
smoking	current	-	-		
	ex-smoker	-	-		
	non-smoker	-	-		
age at UC diagnosis				-	
duration of UC				-	
Montreal classification	E1	-	-		
	E2	-	-		
	E3	-	-		
Mayo-score				-	
F-calpro				-	
P-CRP				-	
B-thromb				-	
P-alb				-	
B-leuk				-	
B-ly				-	
B-neutr				-	
B-hb				-	
Endoscopic findings	yes	-	-		
	no	-	-		

Table 3: Table shell for outcome objectives

Objective	Outcome	Week 8	Week 16	week 24	week 52
1	N patients	N	N	N	N
P1 - a	Proportion of patients on treatment	n (%)	n (%)	n (%)	n (%)
P1 - b	Proportion of patients with clinical remission (full Mayo)	n (%)	n (%)	n (%)	n (%)
P1 - b	Proportion of patients with clinical remission (partial Mayo)	n (%)	n (%)	n (%)	n (%)
P1 - c	Proportion of patients with clinical response (partial Mayo)	n (%)	n (%)	n (%)	n (%)
P1 - c	Proportion of patients with clinical response (full Mayo)	n (%)	n (%)	n (%)	n (%)
P1 - d	Proportion of patients with steroid free clinical remission	n (%)	n (%)	n (%)	n (%)
P1 - g	Proportion of patients with f-calpro reduction ≥50%	n (%)	n (%)	n (%)	n (%)
P1 - g	Proportion of patients with f-calpro reduction ≥75%	n (%)	n (%)	n (%)	n (%)
P1 - g	Proportion of patients with f-calpro reduction ≥90%	n (%)	n (%)	n (%)	n (%)
P1 - h	Proportion of patients reaching f-calpro below 250 mg/kg, of those that had f-calprotectin above 250 mg/kg at baseline	n (%)	n (%)	n (%)	n (%)
P1 - h	Change in f-calpro, among patients with f-calprotectin above 250 mg/kg at baseline	Δ -from baseline (mean ± sd)	Δ-from baseline (mean ± sd)	Δ-from baseline (mean ± sd)	Δ-from baseline (mean ± sd)

Objective	Outcome	Week 8	Week 16	week 24	week 52
P1 - i	Proportion of patients in sustained remission (pMayo) from week 8	-	n (%)	n (%)	n (%)
P1 - i	Proportion of patients in sustained remission (full Mayo score) from week 8	-	n (%)	n (%)	n (%)
P1 - j	Proportion of patients in sustained remission (pMayo) from week 16	-	-	n (%)	n (%)
P1 - j	Proportion of patients in sustained remission (full Mayo score) from week 16	-	-	n (%)	n (%)
P1 - k	Proportion of patients in sustained steroid free remission (pMayo) from week 16	-	-	n (%)	n (%)
P1 - k	Proportion of patients in sustained steroid free remission (full Mayo score) from week 16	-	-	n (%)	n (%)

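### Unlimited carry-forward lets baseline endoscopy and histology decide later full-Mayo and histology outcomes, and Table 3 does not show how many patients were re-examined

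*SAP*

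**What the plan says.** SAP 7.2, for objectives b, c, d, e, g and n, tells the analyst to "define the fulfilment of the remission/response criteria as Yes/No based on the latest available data" at weeks 8, 16, 24 and 52, and then: "Report the proportion of patients on fulfilling the response/remission criteria, not censored at each timepoint". There is no category for a patient who cannot be evaluated. By contrast, objective l works from each Mayo score that exists, and objectives h and t to z from each later measurement.

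SAP 7.1 sets the rule for serial measures: "the latest value will be assumed unchanged until otherwise proven". It gives no time limit, does not say whether a baseline value may be carried, and does not say whether the Mayo score is carried as a whole or by component. It also defines censoring: "Patients will be censored from the study post the last available contact/data entry". Contact of any kind therefore keeps a patient in the denominator.

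SAP 6 states "No imputation for missing values will be performed" and promises the proportion missing only where appropriate. SAP 7.1 repeats that missing values are not imputed, yet calls its own carry-forward rule imputation.

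The full Mayo score includes the endoscopic sub-score (SAP Table 1). Full-Mayo remission needs a total of at most 2, "with no individual sub score exceeding 1 point, with rectal bleeding sub-score of 0" (SAP 2.1). Histology has a code for not determined, with no rule for it under objective n. Protocol 8.9 warns: "All variables or sum variable components are not necessarily available from different electronical health records".

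SAP Table 3 has separate full-Mayo and partial-Mayo rows for remission and response but a single N per week. It has no missing column, although Table 2 has one.

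**The concern.** A full Mayo score needs an endoscopy and a histology grade needs a biopsy. In a retrospective chart study neither is guaranteed near a given week. Under the rules as written, the last examination stands in for the current state however old it is, and it may be the baseline one. A patient whose symptoms have all resolved can then be a full-Mayo non-remitter only because no one repeated the endoscopy. Another patient can remain a success on the strength of one early examination.

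Partial Mayo does not need an endoscopy, so this mechanism does not touch those rows, although they can lack other components. Full-Mayo and partial-Mayo rows printed next to each other under the same N would then differ for reasons unrelated to outcome. The same holds between weeks, between hospitals with different endoscopy practice, and between the extent strata of objective p. The wording about latest available data recurs for the sustained-remission objectives, so the gap carries over to them. Only aggregate results leave the secure environment (Protocol 8.6), so a reader could not rebuild the denominators afterwards.

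**Working it through.** The plan states no expected rate, sample size or power, so there is no figure to reproduce. Steps 1 to 5 follow the SAP definitions. Step 6 is an illustration on assumed inputs.

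**1. Remission, components carried.** Let *e* be the baseline endoscopic sub-score, carried because no endoscopy followed. Take the best case, with the other three sub-scores at 0, so the total is *e*.
- *e* = 3: the total of 3 exceeds 2, and a sub-score exceeds 1. No.
- *e* = 2: the total of 2 is allowed, but a sub-score exceeds 1. No.
- *e* = 0 or 1: all conditions can be met. Yes is possible.

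Across the 4 × 4 × 4 = 64 baseline profiles of the other three sub-scores, remission without a new endoscopy is possible in 0 of 64 when *e* is 2 or 3, and in 64 of 64 when *e* is 0 or 1.

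**2. Response, components carried.** Response needs a fall of at least 3 points and at least 30%, plus the rectal bleeding condition. If the other three sub-scores sum to *S* at baseline and fall to 0, the fall is *S*. The proportional fall is *S*/(*S* + *e*), which is at least 3/(3 + 3) = 50% once *S* is 3 or more. Rectal bleeding of 0 meets its condition. Only profiles with *S* of 2 or less fail: 1 + 3 + 6 = 10. Response is therefore possible in 64 − 10 = 54 of 64 profiles at every *e*. Example: 2 + 2 + 2 + 3 = 9 falls to 0 + 0 + 0 + 3 = 3, which is a response but not remission.

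**3. Whole score carried.** The change from baseline is 0, so response is always No. Remission is No unless the baseline score already met it.

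**4. Histology carried.** Active at baseline stays No. Inactive or normal at baseline counts as Yes with no new biopsy.

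**5. Carried successes.** Inactive histology at week 8 stays Yes at weeks 16, 24 and 52 without another biopsy. A full-Mayo remission at week 8 also stays Yes if the whole score is carried. If components are carried, the endoscopic condition stays met and only new symptom scores can undo the remission.

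**6. Illustration of size.** Assume every unassessed patient is coded No. Let *s* be the share assessed and *r* the rate among those assessed, both assumed. The row shows *s* × *r*. With *r* = 40% and N = 100:

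| Share assessed | Row with N in follow-up (95% Wilson CI) | Among assessed (95% Wilson CI) |
|---|---|---|
| 20% | 8/100 = 8% (4.1 to 15.0) | 8/20 = 40% (21.9 to 61.3) |
| 40% | 16/100 = 16% (10.1 to 24.4) | 16/40 = 40% (26.3 to 55.4) |
| 60% | 24/100 = 24% (16.7 to 33.2) | 24/60 = 40% (28.6 to 52.6) |

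The row alone does not identify *r*: 0.40 × 0.50 and 0.80 × 0.25 both give 20%. With 40% assessed and *r* = 40%, the proportion among all 100 lies between 16% (all 60 unassessed are No) and (16 + 60)/100 = 76% (all are Yes).

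**The case against.** The strongest reply is that no sentence in the SAP codes an unassessed patient as No. Classifying on available data presupposes data. SAP 6 and 7.1 rule out imputation, and SAP 6 promises to report missingness. An analyst could fairly leave a patient with no score out of the proportion. That stands for patients with no usable score and for histology not determined: the SAP is silent, and exclusion is as open as failure. It does not answer the baseline carry-forward, because under SAP 7.1 a carried value is not missing.

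A reader might infer that every full-Mayo and histology row is understated by the share not re-examined. The documents do not support this. Response can be met with a carried endoscopic sub-score (step 2). Active disease is not an inclusion criterion (Protocol 8.2.1), so patients with a baseline endoscopic sub-score of 0 or 1, or inactive histology, can be successes without re-examination. Carried successes push later weeks upward.

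It can also be said that the study is descriptive, that Protocol 8.9 discloses incomplete components, and that an assessed-only denominator is open to selection if re-examination depends on clinical course. All three are true. The disclosure does not tell a reader which denominator lies behind a percentage, and the selection problem is a reason to show two denominators, not to leave the question open.

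**Conclusion.** The point holds as a defect of a stated rule together with a gap. Followed literally, SAP 7.1 and 7.2 make an uncensored patient with a baseline endoscopic sub-score of 2 or 3 a certain full-Mayo remission failure until re-examined, and likewise a patient with active baseline histology for histological remission. They also let old successes persist. Full-Mayo response is automatically No only if the whole score is carried. For patients with no usable score the SAP sets no rule, and its statements on imputation conflict.

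It would go too far to say that these rows measure endoscopy frequency instead of effect. They mix the two, and the net direction is not fixed. The size is unknown, because the documents give neither an endoscopy frequency nor an expected remission rate. The 8%, 16% and 24% figures rest on an assumed 40% rate, on assumed shares assessed, on coding all unassessed patients No, and on no carried successes. To read the 40% as the rate for the whole cohort would further require that re-examination be unrelated to outcome. What does not depend on these assumptions is that one N per week cannot support the full-Mayo and histology rows or their comparison with the partial-Mayo rows.

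**What to change.** Amend SAP 7.1, 7.2 and Table 3 before analysis:
- Do not use the baseline endoscopic sub-score or baseline histology in any post-baseline full-Mayo or histology outcome.
- Treat histology not determined as not evaluable.
- Set an assessment window around each week that limits how long a later endoscopy or biopsy may be carried, and state whether the Mayo score is carried whole or by component.
- Reconcile the carry-forward rule with the statements in SAP 6 and 7.1 that missing values are not imputed.
- In Table 3, give N assessed for each outcome and week beside N in follow-up. Report both n/N assessed and n/N in follow-up, the latter counting unassessed patients as not in remission (or not in response).

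The cost is SAP wording and a wider table shell, with no new data. Assessed denominators will be smaller, and more cells will fall under 5 and so cannot be exported (Protocol 8.6). Patients who are re-examined may differ from those who are not. Showing both proportions makes that visible but does not remove it.

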#### 7.3. Secondary objectives

#### 7.3.1. To Assess the Real-world Effectiveness of Tofacitinib.

- a. Proportion of patients who are taking to facitinib at week 8, 16, 24 and 52.
- b. To assess rates of clinical remission defined by a full or partial Mayo score at week 8, 16, 24 and 52.
- c. To assess rates of clinical response defined by a full or partial Mayo score at week 8, 16, 24 and 52.
- d. Proportion of patients in steroid-free clinical remission at weeks 8, 16, 24, and 52 as defined by full or partial Mayo who did not require any corticosteroid treatment during the period ≥4 weeks prior to the visit (for all patients and for those treated with corticosteroids at baseline).
- e. Proportion of patients reaching clinical response as defined by full or partial Mayo score at week 8, 16, 24 and 52.

- f. Time to response as assessed by a decrease as defined by full or partial Mayo score.
- g. Proportion of responders defined by a f-calpro reduction of  $\geq 50\%$ ,  $\geq 75\%$  or  $\geq 90\%$  at week 8, 16, 24 and 52 compared to baseline.
- h. Proportion of patients reaching f-calpro below 250 mg/kg at week 8, 16, 24 and 52 of those that had f-calprotectin above 250 mg/kg at baseline and change from baseline in f-calpro at week 8, 16, 24 and 52.
- i. Proportion of patients in sustained remission (pMayo and full Mayo score) from week 8 to week 16, 24 and 52.
- j. Proportion of patients in sustained remission (pMayo and full Mayo score) from week 16 to week 24 and 52.
- k. Proportion of patients in sustained steroid free remission (pMayo and full Mayo score) at week 16 to 24 and 52 (for all patients and for those treated with corticosteroids at baseline).
- 1. Change in partial and full Mayo score at weeks 8/16/24/52.
- m. Proportion of patients in sustained endoscopic remission (sub score = 0), mucosal healing (sub score 0-1) or endoscopic response (sub score reduction from baseline of ≥1) from week 8 to week 16, 24 and 52.
- n. Proportion of patients in physician assessed histological remission determined as inactive disease, or normal histology, and change from baseline in histology assessment (0= normal histology, 1= inactive disease and 2 = active disease) at week 8/16/24/52.

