Select only patients that were on remission/steroid free remission at the timepoints. For each patient, define the fulfilment of the remission/response criteria as Yes/No based on the latest available data (at each timepoint 16, 24 and 52 weeks). Report the proportion of patients on fulfilling the remission criteria, not censored at each timepoint.

Secondary objective l:

For each available Mayo score (full or partial), estimate the absolute delta change from baseline value. For each timepoint (week 8, 16, 24 and 52), report the summary statistics (mean, median, sd, 25%Q and 75%Q) of delta change, among patients not censored at each timepoint.

Secondary objective p:

Perform analyses described in secondary objective b and c, stratified by the extent of colonic involvement

Secondary objective q:

For each patient, define the corticosteroid tapering as Yes/No based on the latest available data (at each timepoint 8, 16, 24 and 52 weeks). Additionally, define the tapering rates and doses based on latest available data.

For each timepoint (week 8, 16, 24 and 52), report the proportion of patients that had corticosteroid tapered, among patients not censored at each timepoint. Additionally,

report summary statistics (mean, median, sd, 25%Q and 75%Q) of tapering rates and doses among patients that had corticosteroids tapered.

Secondary objectives r and s:

For each patient, define the fulfilment of the improvement criteria as Yes/No based on the latest available data (at each timepoint 8, 16, 24 and 52 weeks). Additionally, estimate the absolute delta change per baseline value

Report the proportion of patients on fulfilling the response/remission criteria, report the summary statistics (mean, median, sd, 25%Q and 75%Q) of delta change, among patients not censored at each timepoint.

Secondary objectives t-z:

For each subsequent laboratory measure, define "normal-level" as Yes/No variable. Additionally, estimate the absolute delta change per baseline value. For each timepoint (week 8, 16, 24 and 52), report the proportion of patients on fulfilling the "normal-level" criteria and summary statistics (mean, median, sd, 25%Q and 75%Q) of delta change, among patients not censored at each timepoint.

Secondary objective aa:

Report the proportion of patients that received extended induction

Secondary objective bb:

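### Remission, response and marker results at weeks 16 to 52 count values recorded after tofacitinib was stopped or after colectomy as tofacitinib effectiveness

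*SAP*

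**What the plan says.** Protocol 7.3.1 groups these outcomes under the title "To Assess the Real-world Effectiveness of Tofacitinib", and SAP 7.2 analyses them under the same label.

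- **Status rule (SAP 7.2, objectives b, c, d, e, g, n).** For each patient the analyst is to "define the fulfilment of the remission/response criteria as Yes/No based on the latest available data (at each timepoint 8, 16, 24 and 52 weeks"). No condition on being on treatment is attached.
- **Denominator.** "Report the proportion of patients on fulfilling the response/remission criteria, not censored at each timepoint". Objectives h, l, r, s and t to z also use patients not censored at the timepoint. Objective p repeats b and c by extent of colonic involvement.
- **Sustained outcomes (i, j, k, m, o).** Patients are selected on remission status, not treatment status, and then: "Report the proportion of patients on fulfilling the remission criteria, not censored at each timepoint".
- **Censoring (SAP 7.1).** "Patients will be censored from the study post the last available contact/data entry". In SAP Table 1, the date of death or loss to follow-up has the role "Used to define end of follow up". Stopping, switching and colectomy are not mentioned.
- **Serial measures (SAP 7.1).** "Thus for each timepoint, the latest available measure will be used", because the last value is carried forward.

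Stopping or colectomy is handled in three places only. Objective a classes patients recorded as off treatment as discontinued. Objective f defines its time variable as "time from index until response (event) or discontinuation (competing event), or end of data collection (censoring event"). Objective cc makes discontinuation, colectomy and UC hospitalisation a composite event.

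**The concern.** A patient may stop tofacitinib without having responded and later be in remission for another reason. Under the status rule that patient is a week-52 success for remission and response, and also for steroid-free remission if off corticosteroids. After a colectomy, blood markers and the bleeding sub-score may improve because of the surgery, and those values also count. A patient who stops and has no new measurement keeps the last on-drug value, which is then reported as current status.

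There is one cohort and no comparator, so nothing in the tables separates these contributions from results on the drug. At stake is what the week-16, week-24 and week-52 effectiveness rows of SAP Table 3 can be said to describe: the course on tofacitinib, or the state of everyone who once started it. The SAP does not say which is meant.

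**Working it through.** **1. Is stopping a form of censoring?** No. Objective a reports the proportion on treatment among patients not censored. If stopping were censoring, every uncensored patient would be on treatment and objective a would be 100% at every timepoint by construction. Discontinued patients must therefore be in the uncensored group. SAP Table 3 heads the outcome rows with a single N per timepoint.

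**2. One patient under each rule.** Suppose a patient stops at week 10 without a response, stays under follow-up and meets the remission and response criteria at week 52.

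| Objective | How the patient counts |
|---|---|
| a, week 52 | Not on treatment |
| f | Competing event at week 10, so no response event |
| cc | Event at week 10 at the latest |
| b and c, week 52 | In remission; responder |

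The same patient is discontinued before response in f and a responder in c.

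**3. Size.** The plan gives no figure to reproduce. Let d be the share of uncensored patients off tofacitinib at the timepoint, p_on the share in remission among those on drug, and p_off the share counted as in remission among those off drug.

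- As the SAP reports: (1 − d) × p_on + d × p_off
- In remission and still on tofacitinib, same denominator: (1 − d) × p_on
- Excess: d × p_off, whatever the value of p_on

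The documents give none of these inputs. Assumed: p_on = 55%, d = 30–50%, p_off = 20–35%.

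| d | p_off | On drug and in remission | As the SAP reports | Excess (points) |
|---|---|---|---|---|
| 30% | 20% | 38.5% | 44.5% | 6.0 |
| 30% | 35% | 38.5% | 49.0% | 10.5 |
| 40% | 20% | 33.0% | 41.0% | 8.0 |
| 40% | 35% | 33.0% | 47.0% | 14.0 |
| 50% | 20% | 27.5% | 37.5% | 10.0 |
| 50% | 35% | 27.5% | 45.0% | 17.5 |

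With wider assumptions, d and p_off each 20–60%, the excess runs from 0.20 × 0.20 = 4 points to 0.60 × 0.60 = 36 points. If p_off = 0 it is zero.

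**4. Scale.** The 95% half-width for a proportion of 50% is 1.96 × √(0.25/N): 9.8 points at N = 100 and 8.0 points at N = 150. The assumed excess is of similar size to the sampling error, and unlike sampling error it does not shrink with N.

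**5. Which timepoints?** Exclusion criterion 3 removes patients with under 8 weeks of treatment at the start of data mining. If that removes everyone treated for less than 8 weeks in total, almost nobody is off drug at week 8. The effect then lies at weeks 16 to 52.

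**The case against.** The strongest reply is that status at a given week after starting tofacitinib, whatever followed, is a recognised treatment-policy description. Protocol 8.1 plans to determine characteristics before and after use of the drug for all patients. Objective a sits in the same table, so persistence can be read beside remission, and f and cc already deal with stopping. Against a different target, remission among patients still on drug, the direction reverses: with the inputs above that figure is 55%, and the SAP row is 6 to 17.5 points lower. All of this stands. It shows that the excess depends on the target chosen. It does not supply the missing statement of target, and row a beside row b does not tell the reader how many of the remitters were off drug.

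Some stronger conclusions that a reader might draw are not supported:

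- **That the mixing cannot be undone.** SAP Table 1 lists only corticosteroids and 5-ASA as concomitant drugs, so an off-drug remission cannot be credited to a particular replacement drug. But off-treatment status and colectomy dates are collected, so off-drug and post-colectomy values can be separated out.
- **That the protocol expects further treatment lines.** The visible text on treatment lines concerns those before tofacitinib (Protocol 7.3.2).
- **That more patients could appear in remission than on treatment.** With p_on = 55% and p_off = 35%, this requires 0.35d > 0.45(1 − d), that is d > 0.45/0.80 = 56%, outside the assumed range.
- **That all off-drug successes reflect another therapy or surgery.** Carry-forward makes some of them old on-drug values.
- **That colectomy distorts every outcome alike.** A new full Mayo score needs an endoscopic sub-score. The point is strongest for blood markers and bleeding, and no colectomy frequency is given.

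**Conclusion.** The point holds on the text. Objectives b to e, g to p and r to z count values after stopping or colectomy, and values carried past stopping, under a heading that attributes them to tofacitinib. This conflicts with objectives f and cc. Relative to being in remission and still on tofacitinib over the same denominator, the excess is d × p_off: about 6–18 points under the assumed d of 30–50% and p_off of 20–35%. Both ranges are assumptions, and the excess could be zero. The documents do not show that the rows are inflated against every reasonable target; they show that the target is unstated and that the treatment of stopping is inconsistent.

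This should be fixed, but it is not critical. The primary objective is baseline characterisation, there are no hypotheses, and the affected outcomes are secondary and descriptive.

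**What to change.** Amend SAP 7.2 and Table 3 as follows.

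- **Proportions in b to e, g to k, m to p and r to z.** Make the main row the proportion who fulfil the criterion, are on tofacitinib at the timepoint and have had no colectomy before it. Keep discontinued and colectomy patients in the denominator as not fulfilling.
- **On tofacitinib.** Define this by the latest recorded dose at the timepoint, as in objective a, so that a temporary interruption is not a permanent failure. Objective a also regards anyone marked off treatment earlier as discontinued; align that sentence with the same definition.
- **Supplementary row.** Keep the present proportion, labelled as status regardless of treatment.
- **Change-from-baseline summaries.** Show them by treatment status (on drug; off drug or after colectomy) with n in each group. Note that the on-drug summary describes only patients who persisted and is therefore selected.

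The cost is SAP wording, one flag derived from the dose and colectomy fields already in Table 1, and a few extra table rows. No new data are needed. The week-24 and week-52 proportions in the main rows will look less favourable wherever off-drug patients would have counted as successes. Marker rows need a clear label, because a patient with a normal measured value after stopping will appear as not fulfilling the on-tofacitinib criterion.
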